4.3 Participant discontinuation and withdrawal

4.3.1 Discontinuation and withdrawal at the choice of the participant

Participants in the study can freely withdraw their informed consent at any time and be treated according to the department's standard procedures. Patients will be excluded from the study if they withdraw their consent and will be informed that withdrawal from the study will not affect their future treatment. If possible, the reason for withdrawal will be obtained and reported. The patient is not obligated to give reasons for withdrawal. Patients who leave the study will be asked for permission to continue to collect data and to use already collected data. If the patient gives permission, he/she will be included in the final analysis. Only if the patient refuses the use of already collected data, all data relating to him/her, will be destroyed.

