7.1 Primary outcome

Feasibility outcomes include:

Recruitment and retention rates. The recruitment rate will be determined by the number of individuals who participate in the study out of those who are eligible/admissible but refused to participate. First, we will evaluate the number of patients we are able to include in the study during the inclusion period. A proportion of 60% or more of patients awaiting elective CABG surgery who are eligible for the study is acceptable. Retention will be assessed by the percentage of participants who remain in the study from beginning to end of study (30 days post-surgery).

Attrition rates. Attrition is defined by the number of individuals who give consent to participate in the study but drop out before the end of the intervention period, regardless of group allocation.

Fidelity. Fidelity of delivery of the webcam-based exercise training intervention will be assessed qualitatively by 8-10 semi-structured interviews the day before surgery by a research nurse.

Adherence rates. Adherence to the interventions will be measured by using the number of telephone counselling and tele-exercise sessions delivered out of the theoretical number that could have been delivered based on the surgical wait time of each participant. Adherence to the homebased tele-exercise training sessions and telephone counselling by evaluating the number of sessions applied in the intervention group. This will be collected by patient recorded physical activity logbook, by weekly phone calls and completed by accelerometer data. Adherence with the prehabilitation program will be assessed against the target of individuals achieving > 70% of the prescribed exercise program (self-reported) + during the study follow-up with phone calls. Inclusion in the CABGpreHAB study must be attractive to at least 30% of eligible patients who meets the inclusion criteria. The interventions must be widely accepted, with at least 70% of included participants completing 70% or more of the planned sessions in the intervention group. This will be assessed by interviews addressing reasons for withdrawals from the study and at which stage of the study these occur.

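### Read literally, the data-destruction rule in section 4.3.1 conflicts with the attrition, retention and adherence rates in section 7.1, and any effect favours feasibility

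*Protocol*

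**What the plan says.** Protocol section 4.3.1 sets three rules for a participant who leaves:

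- On withdrawal of consent: "Patients will be excluded from the study if they withdraw their consent".
- Leavers are asked whether their data may be used. "If the patient gives permission, he/she will be included in the final analysis".
- For the rest: "Only if the patient refuses the use of already collected data, all data relating to him/her, will be destroyed".

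The same section adds: "If possible, the reason for withdrawal will be obtained and reported".

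Section 7.1 lists the primary feasibility outcomes. Attrition is "the number of individuals who give consent to participate in the study but drop out before the end of the intervention period", counted in both arms. For retention: "Retention will be assessed by the percentage of participants who remain in the study from beginning to end of study", which is 30 days after surgery. Acceptance of the intervention is judged "with at least 70% of included participants completing 70% or more of the planned sessions in the intervention group". The end of section 7.1 adds a condition for a larger trial: at least 52% of the intervention group must receive more than 60% of the intended interventions. None of these definitions makes an exception for leavers who refuse use of their data.

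Section 9.1 plans to report dropout rates and the reasons for dropout, and section 3.2 refers to a CONSORT flow diagram. The sample size in section 3.6 is 25 per group.

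**The concern.** Section 4.3.1 ties inclusion in the analysis to permission and exempts nothing from destruction, not even the bare facts that someone consented, was allocated to an arm and left. Section 7.1 needs exactly those facts. Staff who follow section 4.3.1 to the letter cannot compute the section 7.1 rates over all who consented, and the protocol does not say which instruction gives way.

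The conflict touches only leavers, so the loss would be selective. A refuser who left during the intervention period would drop out of both numerator and denominator of attrition, and out of the denominators of retention and adherence. All three rates would then look better. In an arm of 25, one person can decide whether a stated criterion is met.

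**Working it through.** The protocol states no dropout or refusal rate, so there is no figure of its own to reproduce. The following is sensitivity arithmetic under the literal reading, in which a refuser disappears from every count.

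**Inputs.** From the protocol: N = 50 in total, n = 25 per arm (section 3.6), and the 70% and 52% criteria (section 7.1). Assumed: d leavers during the intervention period, k of them refusing use of their data, s participants in the intervention arm who reach the session target, and no later losses.

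**Attrition and retention.** Attrition moves from d/N to (d − k)/(N − k), and retention from (N − d)/N to (N − d)/(N − k). Since N(d − k) − d(N − k) = −k(N − d), attrition can only fall while anyone remains.

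- d = 5, k = 2: attrition 5/50 = 10.0% becomes 3/48 = 6.2%; retention 90.0% becomes 45/48 = 93.8%.
- d = 10, k = 2: attrition 10/50 = 20.0% becomes 8/48 = 16.7%; retention 80.0% becomes 40/48 = 83.3%.
- Attrition 20%, with 5% to 50% of leavers refusing: 0.5 to 5 records are expected to be destroyed, and observed attrition is 9.5/49.5 = 19.2% down to 5/45 = 11.1%.

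**Adherence and delivery criteria.** Removing k participants who missed the target moves s/25 to s/(25 − k).

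- 70% rule: 0.70 × 25 = 17.5, so 18 are needed. 17/25 = 68.0% fails; 17/24 = 70.8% passes after one removal.
- 52% rule: 0.52 × 25 = 13 are needed. 12/25 = 48.0% fails; 12/24 = 50.0% still fails; 12/23 = 52.2% passes after two removals.

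**Chance of meeting the 70% rule.** With X binomial (25, p) and every removed person a non-completer, the rule needs X ≥ 18 with no removal, X ≥ 17 with one (0.70 × 24 = 16.8) and X ≥ 16 with three (0.70 × 22 = 15.4).

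| True adherence p | k = 0 | k = 1 | k = 3 |
|---|---|---|---|
| 0.55 | 6.4% | 13.4% | 24.2% |
| 0.60 | 15.4% | 27.4% | 42.5% |
| 0.65 | 30.6% | 46.7% | 63.0% |

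**With the count kept.** Attrition stays d/50, retention stays (50 − d)/50, and the adherence denominator stays 25. The sample size does not change.

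**The case against.** The strongest reply is that nothing in the protocol removes refusers from the rates. Section 4.3.1 destroys data; it does not redefine a denominator. The attrition definition covers everyone who consents and then drops out, a flow diagram and dropout numbers are planned, and a head count needs no personal data. A sensible team could count the person as a dropout, and in the intervention arm as a non-completer, without any session record. Denominators are also commonly settled in the statistical analysis plan, which is not shown. This stands as far as it goes: removal is an inference from the literal wording. But an analysis plan cannot restore a fact that has been destroyed. Whether a count survives depends on the protocol and the consent given under it.

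The examples are also chosen close to the thresholds, and attrition and retention have no pass mark, so a shift in them crosses no stated line. Both points stand.

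A reader might infer that adverse events already reported would be lost. The documents do not support that. Serious events in the intervention period go to the ethics committee within 7 days, with annual reports of adverse events (section 10.2.3). Adverse events in that period are documented from the patient record (section 8.2), and source data sit in that record or on worksheets (section 11.1).

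A reader might also suppose that refusers are the least satisfied dropouts. The protocol gives no data on this.

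Finally, keeping arm, stage, reason and event type for each refuser could identify people in a single-centre study of 50, and would retain part of what they refused. This stands, and it limits the remedy to a bare count.

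**Conclusion.** The point holds as a conflict between two sections, not as a demonstrated bias. As worded, section 4.3.1 would take refusing leavers out of rates that section 7.1 defines over all who consent or are included, and no section reconciles the two. It would be too strong to say that the protocol does exclude them from the rates.

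The direction is one-sided for anyone who leaves during the intervention period. For adherence, it rests on the leaver having missed the session target, which is likely but not certain. The consequence is greatest for the intervention-arm criteria, where one removal can turn a fail into a pass on the 70% rule and two can do so on the 52% rule. The size in practice is unknown: it depends on how many leavers refuse, and the 5% to 50% range is an assumption. If nobody refuses, nothing changes. The wording should still be corrected, because the correction is cheap and must be in place before anyone withdraws.

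**What to change.** In section 4.3.1, and in matching words in the patient information, state that for a leaver who refuses use of data already collected:

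- all individual-level data are destroyed, as now;
- only a bare anonymous count of consent, allocation by arm and withdrawal is kept;
- the person stays in the denominators for retention, attrition and adherence, counted as a dropout and, in the intervention arm, as a non-completer.

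Qualify the sentence on inclusion in the final analysis to agree with this. The cost is one sentence in each document and, at most, slightly less favourable retention and adherence figures. Because the count holds no stage of withdrawal or session record, a refuser who left late would be scored as an ordinary dropout and non-completer. That errs against feasibility rather than for it.

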4.3.2 Discontinuation and withdrawal at the choice of the investigator

The project team reserves the authority to halt the participation of any individual involved in the study, primarily in response to adverse events and concerns regarding safety. Additionally, the principal investigator retains the right to conclude the study. Grounds for such termination may encompass inadequate adherence to the study's protocol, challenges in participant recruitment, deviations from the established timeline, and administrative discrepancies.

5. Study site and personnel

5.1 Study site and setting

The CABGpreHAB feasibility study will be carried out in The Department of Cardiothoracic Surgery at The Heart Centre, Copenhagen University Hospital, Rigshospitalet, Copenhagen.

5.2 Study personnel

In the CABGpreHab study, the interventions are administered by trained specialist nurses specializing in heart surgery and specialized physiotherapists. To execute the interventions effectively, the nursing staff will undergo skills enhancement through training courses and supervised practice, particularly given the nature of the psychosocial interventions involved. The physical exercise program is initiated by physiotherapists with specific expertise in exercise training for patients awaiting CABG surgery. The principal investigator is [name], [name] is primary responsible physician/surgeon and [name] is project leader.

6. Study interventions

All included patients will receive standardized surgical processes and perioperative care under existing protocols for preoperative patient education.^{23,68}

6.1 Control intervention/Usual care

Participants assigned to the control group will receive usual care including standard information about CABG surgery, pre- and postoperative care, and postoperative physical activity advise.⁶⁸ Patients are informed about date of surgery along with information in secure mailbox (e-Boks) after the MDT conference. The date for surgery is tentative, and there will always be some risk of postponed surgery for the elective patient due to emergency heart surgery. Patients are either admitted the day before surgery or weeks before in our pre-ambulatory clinic in the Department of Cardiothoracic Surgery at Rigshospitalet. They receive written materials and links to animated videos about preparing for surgery is available for all patients undergoing elective CABG surgery.⁶⁹⁻⁷¹ The day before surgery the patient is informed by their heart surgeon and the last assessment and preparation for the surgery takes place in the ward. The patients have also been given information about the surgery and the postoperative period during their pre ambulatory visit weeks before surgery. This preparation includes counselling with a multi-disciplinary team, including a nurse from the department, a physiotherapist, cardiothoracic anesthesiologist, and surgeon. During this preoperative counselling session, the nurse assesses nutrition status, as well as smoking and alcohol habits. The nurse also invites the patient to talk about the situation of being a heart patient awaiting surgery. Preoperative anxiety is assessed with The Apais tool to encouraged patients to talk about uncertainty and further needs for information. The nurse also provides information related to postoperative expectations such as the ICU, the

operation room, and issues related to the postoperative period in the department, such as pain, arrhythmia, pulmonary issues, coughing, early mobilization and so on. Furthermore, if patients are consuming high levels of alcohol, we contact the “social care nurse at Rigshospitalet”, who can plan with the patient to be abstinent before surgery. This preoperative preparation where patients and significant others are invited to participate is a well-established practice in the Department of Cardiothoracic Surgery following protocols and guidelines in the field.^{23,68}

6.2 Multimodal prehabilitation interventions (CABGpreHAB)

Patients randomized to the multimodal prehabilitation programme will besides usual care as described above receive preoperative interventions that consists of:

6.2.1 Exercise intervention

During the initial assessment patients will be taught how to perform the exercises to complete at home during the intervention period. The exercise intervention is supervised by skilled physiotherapists and delivered via Infinity Connect app and a webcam⁷² at Rigshospitalet to a group of approximately 4–8 patients who exercise at home and communicate via a tablet. Each session is 60 min, i.e., 40 min of exercise and 20 min of patient education, three times per week for the prehabilitation period. The exercises used in the program are identified and selected amongst exercises used in previous exercise intervention studies and involves larger muscle groups with 50/50% exercises for upper and lower extremities, respectively.⁷³ The exercises are executed in four sets to achieve peripheral muscle fatigue and secondary dyspnea/breathlessness. Each set is carried out in a predefined period of 20 to 40 s with a maximum number of repetitions performed, i.e., 8 to 25 repetitions depending on the patients exercise capacity and motivation, but with the aim of 12 to 20 repetitions.^{73,74} In practice the training intensity is determined by using the self-rated Borg Scale, moderate intensity RPE 11-15, 50-60% VO₂peak.⁷⁴

The first week serve as a familiarization phase with the purpose to adapt to exercising, adjusting, and optimizing load and to avoid musculoskeletal overload injuries. Monitoring physical activity and providing motivation through phone calls weekly will be enhanced by incorporating a novel accelerometer system, offering activity level feedback (SENS innovation)⁷⁵ to guide healthcare staff. Participants in the intervention will be instructed to perform daily exercise tasks such as brisk walking and sit-stand exercises. Additionally, motivational phone calls will be made to participants in the intervention group, while healthcare staff will receive feedback on these patients, aiding to guide them in achieving their activity goals. Patients will also be asked to complete a diary describing physical activity outside the programmed session, included in a patient booklet. All study participants will wear the accelerometer from the screening phase until the day preceding the procedure, and again postoperatively until the day of discharge and for 30 days

thereafter.^{76,77} The technology platform provided to the patients includes a tablet and an accelerometer device to facilitate exercise training sessions and data collection.

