3.3 Randomization

Following baseline assessment, randomization will occur in a 1:1 ratio, stratified by age, gender (men, women), and EuroSCORE (indicative of disease severity), assigning participants either to the intervention group or to usual care. Randomization is completed using the web-based tool Randomizer for Clinical Trials.

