3.5 Participant timeline

After the MDT conference eligible patients identified from the elective waiting list for CABG-surgery are invited to participate. When they have contended, they will be allocated to either CABGpreHAB plus usual care or usual care alone. The intervention will be launched immediately after inclusion in the study. At baseline a face-to-face introduction and counselling will take place at the preoperative clinic at the Department of Cardiothoracic surgery Rigshospitalet. There will be assessment at baseline, the day before surgery (ending of the intervention period) and on day 30 post surgery. All study participants will wear the accelerometer from the screening phase until the day preceding the procedure, and again postoperatively until the day of discharge and for 30 days thereafter as illustrated in **Figure 2**.

[figure not shown]

Figure 2. Graphical illustration of the study design

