Following the MDT conference in the department of Heart and Lung Surgery, Rigshospitalet the responsible surgeon screen for eligibility by comparing patients' referral against the inclusion and exclusion criteria as described in this protocol section 4.1. If the patient is deemed eligible after screening, they will receive an invitation in e-Boks to be contacted for a brief information about the study. If they accept this invitation, the patient will be contacted by telephone by a responsible clinician in the project, and if the patient is interested to hear more, written information material about the study will be send by e-Boks or regular post. The patient will be informed that participating is voluntary, that they have the right to bring a bystander for the oral information, which will take place when they meet for the planned visit in the pre-clinic some days later. If patients haven't got the invitation about information in E-boks the responsible surgeon will introduce the study for eligible patients and present patients with the written information at the meeting in the pre-clinic. The oral information will be given with no external interruptions and will be given in a language easily understood without technical or value laden terms. The patient will receive a full explanation of the study design and study procedures, and information about usual care. This information interview is performed by the principal investigator or in her absence by a designated delegate. Consent to participation is given on the basis of written and oral information. Prior to consent, it must be ensured that a potential participant has been given sufficient time to consider his or her participation and minimum 24 hours. However, potential participants can sign earlier if they wish. An informed consent form must be signed and dated by the participant prior to participation in the trial. A copy of the form is provided to the participant. The principal investigator and her designated delegates can receive the signed consent form. When the written informed consent is received, the study specific procedures such as test, randomization and other study related procedures will take place.

Patients will be eligible if they comply with the inclusion criteria in line with previously used criteria.^{66,67} Exclusion criteria are listed below.

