Alcohol intake status	Self-reported	Alcohol intake status assessed as change from baseline. The number of participants successfully quitting alcohol consumption out of all participants consuming alcohol.
Patient characteristics	Self-reported	Age, gender, educational level, employment, civil status
CR status	Self-reported	Last follow up (30 days post index surgery) questionnaire ask about status for: Participating in CR
Other outcomes DATA		
Adverse Events	Patient record	Measuring outcomes related to adverse events for ensuring patient safety
Complications PO	Patient record	Complications such as pneumonia, atelectasis, hemorrhage, cardiac arrhythmias, delirium
ICU-LOS/LOS	Patient record	Indicator of how well patients are recovering post-surgery and may indicate complications.
DAOH ₃₀	Patient record	DAOH ₃₀ . ^{100,101} Days alive and out of hospital is a composite measure that can be calculated based on available variables and proposed as a reliable surgical endpoint. DAOH integrates several clinical outcomes, including death and hospital readmission.
Biomarkers	Patient record	Hgb, albumin, kreatinin, CRP planned as standard blood work at baseline and post intervention.

Abbreviations: BMI: Body Mass Index; BIA: bio electrical Impedance Analysis, CR: cardiac rehabilitation; DAOH₃₀: Days alive out of hospital₃₀; HRQoL: Health related quality of life; ICU: Intensive care unit; ICU-LOS: intensive care unit – length of stay; LOS: length of stay; NRS 2002: Nutritional Risk Screening 2002; PO: post operative; PAM₁₃: Patient activation measure; PHQ-4: Patient Health Questionnaire for depression and anxiety; SF-12: Short form survey.
		

8. Data collection

Clinical and sociodemographic data as well as patient-reported outcome measurements will be collected for both groups at baseline, the day before surgery, and 30 days post-surgery as shown in **Table 2**.

TABLE 2 Schedule of enrollment, intervention, and assessment

Timepoint	Enrollement Allocation Eligibility	Baseline assessment	Min 2 weeks Homebased Prehabilitation	The day before surgery	Surgery	4 days PO	30 days post index surgery
	T ₋₁	T ₀	T ₁	T ₂	T ₃	T ₄	
Eligibility screening	X						
Informed consent, enrollment		X					
Medical history ¹ , social demographics ²		X					
Intervention + Usual care			X				
Primary Outcome							
Feasibility		X		X			X
Secondary Outcomes							
6MWT (functional capacity)		X		X			X*
BIA + NRS-2002 (baseline only)		X		X			
Hand grip strength		X		X			

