8.1 Data from questionnaires

The questionnaires are self-administrated and will be completed electronically in REDCap a web-based data capture tool¹⁰³ which meets the data legislation for logging. The study participant will receive an email with link to a website through which questionnaires can be completed. The e-mail contains a login and password for the trial participant's access. If patients do not complete the questionnaire electronically, the paper questionnaires will be handed out to the patient, and independent study personal then enters the responses into REDCap. Participants will complete the questionnaires at all three time points: baseline, the day before CABG surgery after the intervention, and 30 days post-surgery. The filled-out questionnaires typed in REDCap and responses will be stored in a secure folder with limited access ("lovbeskyttet mappe").

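### The protocol gives inconsistent orders for baseline assessment and allocation, so self-reported baseline values could be recorded after patients know their arm

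*Protocol*

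**What the plan says.** Five parts of the protocol bear on the order of events.

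- Section 3.3 (Randomization): "Following baseline assessment, randomization will occur in a 1:1 ratio".
- Section 4 (Selection and allocation of participants): once written consent is received, "the study specific procedures such as test, randomization and other study related procedures will take place".
- Section 3.5 (Participant timeline): "When they have contended, they will be allocated to either CABGpreHAB plus usual care or usual care alone" (the verb is evidently meant to be consented). Then "The intervention will be launched immediately after inclusion in the study", and after that "At baseline a face-to-face introduction and counselling will take place at the preoperative clinic".
- Section 6.2.1 (Exercise intervention): "During the initial assessment patients will be taught how to perform the exercises to complete at home during the intervention period". The term 'initial assessment' is not defined.
- Section 8, Table 2: the first column is headed "Enrollement Allocation Eligibility". The baseline assessment is a separate column after it, and informed consent is marked under baseline.

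On the questionnaires, section 8.1 says "The study participant will receive an email with link to a website through which questionnaires can be completed", with paper forms as a fallback. Section 3.4 states that patients and treating staff cannot be blinded, and that physical testing and data collection are done by blinded staff.

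**The concern.** In an open-label trial, baseline values protect the comparison only if they are recorded before the patient, and whoever tests the patient, knows the arm. A patient who has just learned of the allocation, or has just had a first counselling session aimed at stress and anxiety (section 6.2.3), may answer a quality-of-life or anxiety questionnaire differently. State anxiety is the most exposed, because Table 1 describes it as a rating of how the person feels at that moment.

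These values are used. Table 1 defines the 6MWT, sit-to-stand, accelerometer activity and SF-12 as change from baseline. Section 9.1 plans a repeated-measurements analysis of change over time, including quality of life, depression and anxiety, and estimates of improvement in patient-reported outcomes against usual care. Section 2.2 says the outcome data will inform the sample size of the future RCT. Because section 3.1 presents this study as a test of the methods for that RCT, an ambiguous sequence could also be carried forward into it.

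**Working it through.** The question is one of sequence, so the check sets the statements side by side.

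1. **Baseline, then allocation.** Section 3.3 says so directly. Section 4 names tests before randomization in its list of procedures after consent. The two agree.
2. **Allocation, then baseline.** The Table 2 heading puts allocation in the column before baseline. Read literally, it also puts allocation before consent, which section 4 rules out. Section 3.5 narrates consent, allocation and immediate launch, and only then the introduction and counselling at baseline. It does not place baseline measurement between consent and allocation.
3. **Intervention content labelled as baseline.** Section 6.2.1 puts exercise teaching in the initial assessment. Section 6.2.3 has a baseline consultation, and section 6.2.4 hands out nicotine replacement at the baseline counselling session. If baseline here means the baseline assessment of section 3.3, these elements would precede randomization, which cannot be intended.
4. **What 'initial assessment' could mean.** Table 1 uses the phrase for fitting the accelerometer, which all participants wear; that suggests the baseline visit. Section 10.3 describes a physiotherapist's assessment before the exercise component starts; that would suit teaching after randomization. The text does not settle it.
5. **Questionnaires.** Table 2 marks SF-12, HeartQoL, PHQ-4 and the anxiety inventory at baseline. Section 8.1 delivers them by emailed link and sets no condition that they be complete before the arm is disclosed. Under step 1 the order follows by implication from section 3.3. Under step 2 nothing prevents late completion.

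**How a late baseline would act.** Suppose learning the arm moves one arm's mean baseline by *d*. The between-arm difference in raw change then moves by *d* in size. With adjustment for baseline and a slope *b* between 0 and 1, it moves by *b* × *d*, which is smaller but not zero. As a yardstick, with 25 per arm the standard error of a difference in mean change is √(2/25) = 0.283 standard deviations of change, so a shift of about 0.28 of those would equal one standard error. The protocol gives no information on *d*, so this is a scale and not an estimate of the bias.

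**The case against.** The best defence is that the operative text is sound. The dedicated randomization section and the consent procedure in section 4 agree on tests first. Section 3.5 says only that allocation follows consent, which remains true when baseline tests come in between, and its baseline sentence concerns introduction and counselling, not outcome measurement. Table 2 is weak evidence: as read it has seven column headings, six time labels and no allocation row, so its first heading may be a loose label. Much of this stands. It shows which order is probably intended, but it does not remove the conflict between the Table 2 heading and section 3.3, or define the initial assessment.

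A reader might infer something stronger: that either controls are taught the experimental exercises or baseline must be recorded after allocation. The documents do not support this. The opening of section 6.2 limits its content to patients randomized to the programme, and section 6.1 lists no exercise teaching for controls. A single visit running tests, randomization and then teaching of the intervention arm fits sections 3.3, 4, 6.2, 6.2.1 and 10.3, provided the initial assessment means the whole visit or the physiotherapist's assessment. Contamination of the control arm is therefore not a stated plan.

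It is also fair to say that the feasibility rates in section 7.1 do not depend on change from baseline, and that the clinical outcomes are labelled explorative.

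**Conclusion.** The inconsistency is real and should be corrected. Sections 3.3 and 4 give the sound order. The Table 2 heading contradicts it, section 3.5 narrates a different one, and section 6.2.1 places intervention content in an undefined assessment. The consequence is conditional: if site staff work from Table 2 or section 3.5, unblinded patients can give baseline self-reports after learning their arm, and a baseline tester may know it too. Bias would then enter the explorative change-from-baseline comparisons and the estimates carried to the RCT. Its size and direction cannot be determined from the documents. This is a moderate point that is nearly free to fix; it does not threaten the recruitment, retention or adherence results.

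**What to change.** Write one sequence into sections 3.3, 3.5, 6.2.1 and Table 2:

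1. written consent;
2. all baseline physical tests and questionnaires completed, on a tablet or on paper at the pre-clinic if the emailed link has not been used;
3. randomization;
4. exercise teaching and first counselling, for the intervention arm only, by staff other than the blinded tester.

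In Table 2, move allocation to after the baseline assessment. In section 6.2.1, replace the reference to the initial assessment with 'After randomization', and use the word baseline in sections 6.2.3 and 6.2.4 consistently with this order. In sections 3.3 and 8.1, state that a participant can be randomized only once baseline is recorded as complete, for example through a check in REDCap.

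The cost is protocol wording, a simple database check and a slightly longer pre-clinic visit. Sample size and outcomes are unchanged.
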